1. STUDY OBJECTIVES

Our *Primary objective* is to determine the safety and dose-response of target engagement for treatment with escalating doses of candesartan in those with mild cognitive impairment (MCI) and Alzheimer's disease (AD).

Our *secondary objectives* are to assess the efficacy of 1 year treatment of candesartan on biomarkers of vascular function, neurodegeneration, and neuro-inflammation; to assess the efficacy of 1 year treatment with candesartan on amyloid imaging; and to estimate the effect size of Candesartan on cognitive and functional measures in MCI and AD.

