7.4. FOLLOW-UP FOR ADVERSE EVENTS

All AE/SAE's will be recorded in the participant chart with start/stop date. The study physician may perform additional evaluations, visits, phone communication, repeat blood testing, or refer to the emergency room or the participant healthcare provider for medical care if necessary. If the event results in intervention discontinuation and/or study withdrawal, the participant will be followed for 2 months post-withdrawal with a monthly phone call. They will also be invited to perform the final visit evaluation including all study procedures planned for that visit if the participant has been in the study more than 5 month post baseline evaluation.

Follow-up on reported symptoms of hypotension or a BP<100/40 mm Hq: When a subject notifies the study team that they have either symptoms suggestive of hypotension (dizziness, weakness, near syncope, or syncope) or that their blood pressure is less than 100/40 mm Hg, the study physician will review the incident and determine if the subject is safe to continue in the study. The physician may discontinue the study medication immediately, elect to lower the dose of the study medication, ask subject to present to the study center for a safety evaluation, and/or monitor the subject blood pressure. The subject may continue in the study if blood pressure is >100/40 mm Hg on the lower dose of the study medication and had resolution of symptoms. In those on 16 mg and 32 mg, the doses will be decreased to the next lower dose. Those on 8 mg of candesartan, a trial of every other day 8 mg of candesartan will be attempted prior to discontinuation.

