9.3. DATA ANALYSIS

 Table 2 provides a list of main outcomes.

Table 2: Independent, main outcome and other variables to be used in the analyses		
Independent:	Group (Candesartan vs placebo)	
Safety outcome:	hypotensive episodes, symptoms (dizziness, weakness, cough) , creatinine >2.5 mg/dl , K>5.9 mEq/dl, number of discontinuations of candesartan, AE, SAE, Deaths	
CSF outcomes:	CSF tau, inflammatory proteins	
Vascular outcomes:	PWV, augmentation index	
Imaging outcomes:	Perfusion, hippocampal volume, vasoreactivity, Global SUVR (PiB and T807)	
Cognitive outcomes:	CDR, EXAMINER, HVLT, TMT (B and B-A)	

Baseline characteristics including demographic, APOe, social and cognitive measures will be compared between the 2 groups to assess randomization fidelity. The list of the main variables is shown in Table 3. We will compare the change in our outcomes over the study period between the treatment and placebo arms using Mixed Models. For the dose response analysis, the dose vs RAS activity will be plotted to explore the degree of modulation for each Ang peptide at the various doses.

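### The mixed model of change, the only between-arm analysis in Section 9.3, does not suit one-time or sparse safety events, and no other by-arm safety summary is specified

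*Combined protocol and SAP*

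**What the plan says.** Section 1 states that the primary objective "is to determine the safety and dose-response of target engagement for treatment with escalating doses of candesartan". In Section 9.3, Table 2 gives treatment group as the independent variable and lists the safety outcomes as "hypotensive episodes, symptoms (dizziness, weakness, cough) , creatinine >2.5 mg/dl , K>5.9 mEq/dl", followed by "number of discontinuations of candesartan, AE, SAE, Deaths".

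The one between-arm method for outcomes is in the text below the table: "We will compare the change in our outcomes over the study period between the treatment and placebo arms using Mixed Models". It does not say whether the models are linear or generalized, and it gives no link, covariance structure or summary measure.

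No other section supplies a safety method. Section 9.1 names intention-to-treat and per-protocol analyses but no safety set. Section 7.2 describes how adverse events are logged and graded. Section 7.3 promises the DSMB a yearly summary of adverse events and deaths, without a method and without saying that it is by arm. The dose plot in 9.3 concerns renin-angiotensin activity, not safety. For an event that leads to stopping, Section 7.4 says "the participant will be followed for 2 months post-withdrawal with a monthly phone call"; it also invites those more than 5 months past baseline to the final visit.

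**The concern.** A mixed model of change needs repeated values of the same quantity in each person. Death, stopping the drug, and ever having an SAE give one yes-or-no record per person. The laboratory thresholds come close to that. Section 4.2 excludes creatinine above 2.0 and potassium above 5.5, so the indicators for 2.5 and 5.9 are zero at screening, and change is simply whether the crossing occurred.

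Such events are also likely to be few. If they fall in one arm only, the pattern of most interest for harm, the stated method either fails or returns a result that depends on how the software treats an unidentified model. The event measure, denominator, interval and rule for repeat events would then be chosen after the data are seen, on part of the primary objective. There is a smaller problem in Table 2: its discontinuation item names candesartan, so read literally it counts one arm only.

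**Working it through.** **Inputs.** The sample size is 72 (Précis) with 1:1 allocation (Section 5.1), so 72/2 = 36 per arm. The documents give no significance level, power, effect size or event rate, so 72 cannot be reproduced, and every event rate below is an assumption.

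**1. One record per person.** Take 2/36 v 0/36 as an example.
- Risk difference: 2/36 − 0/36 = 0.056.
- Linear mixed model with a random intercept: standard error 0.029, z = 1.894, p = 0.058, with a warning that the Hessian is not positive definite. With one record each, the between-person and residual variances enter only as a sum. The software split that sum into two equal parts of 0.0135, and the data cannot say whether that is right.
- Ordinary regression on the same data: pooled variance (2 − 4/36)/70 = 0.0270; standard error √(0.0270 × 2/36) = 0.0387; t = 0.0556/0.0387 = 1.43; p = 0.156.
- Fisher's exact test: p = 0.49.
- Logistic model: no convergence, with a standard error of about 5,486, because the placebo arm has no events.

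The value 0.058 is therefore an artefact of an unidentified model, not evidence about the drug.

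**2. How often an arm is empty.** For a common rate p in both arms, let q = (1 − p)^36. The chance that at least one arm has no event is 1 − (1 − q)².

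| Assumed rate | q, a given arm empty | At least one arm empty | Both arms empty (q²) |
|---|---|---|---|
| 1% | 0.70 | 91% | 48% |
| 2% | 0.48 | 73% | 23% |
| 5% | 0.16 | 29% | 2% |

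In all of these trials the maximum-likelihood log odds ratio has no finite value.

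**3. What a simple summary gives.** For 4/36 v 0/36 the odds ratio is infinite. The risk difference is 4/36 = 11.1%, with a Newcombe 95% CI of −0.6% to 25.3%, and Fisher p = 0.115.

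**4. Where a mixed model can work.** Two titration visits and months 3, 6, 9 and 12 give 6 post-baseline visits, so 36 × 6 = 216 visit records per arm. At an assumed 5% per visit, 216 × 0.05 = 10.8 events are expected in an arm, and if visits were independent the chance of none is 0.95^216, about 0.00002. A random-intercept logistic model gave a finite group effect in 30 of 30 simulated trials at 10% v 20% per visit, and in 30 of 30 at 5% v 15%. Those fits used a prior, which itself keeps estimates finite, so the event count is the stronger evidence.

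**5. Unequal observation.** Suppose a proportion d stops at a mean of m months and is then followed for 2 months by phone. Person-months per arm are 36 × [12(1 − d) + d(m + 2)].
- m = 6, 10% v 5% stopping: 417.6 v 424.8, ratio 0.98.
- m = 3, 20% v 5%: 381.6 v 419.4, ratio 0.91.
- m = 1, 30% v 5%: 334.8 v 415.8, ratio 0.81.

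The range is illustrative only, since the stopping times and proportions are assumed. It also ignores the final visit offered after 5 months.

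**The case against.** The strongest reply is that 9.3 says mixed models, not linear ones, so generalized models are not excluded. Blood pressure, creatinine and potassium have screening or baseline values and are measured repeatedly. This stands: for visit-level indicators with enough events in both arms, a generalized mixed model is usable. A reader might infer that the stated method cannot be fitted to any safety outcome, but the documents do not support that.

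A reader might also infer that the primary safety objective has no workable comparison. That too goes beyond the documents. Arms are randomised, group is the stated independent variable, and adverse events are logged with dates, seriousness and severity, so by-arm incidence can be computed. What is missing is a statement of how.

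A third tempting reading is that raw counts would understate harm on candesartan by a definite amount. The plan does not say that raw counts will be used. Any such figure depends on assumed stopping and on a constant event rate, whereas dose escalation takes place in the first weeks. Someone who stops because of an event has already been counted as having it.

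The reply does not rescue deaths, discontinuations and ever-SAE, which have no repeated measure under any mixed model, or threshold crossings that leave an arm empty.

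**Conclusion.** The point holds in a limited form. Section 9.3 applies one method to all main outcomes, and that method does not suit one-time or sparse safety events; nothing elsewhere fills the gap. The mismatch follows from the text alone. How often it would bite depends on event rates that the plan does not give: at least one arm would be empty in 29% to 91% of trials for rates of 5% down to 1%, assuming the same rate in both arms and 36 analysed per arm. The p-value of 0.058 against 0.49 is one worked example from one software package, not a general error rate. The exposure ratio of 0.98 to 0.81 supports reporting rates as well as proportions but does not establish a bias. The gap affects analysis and reporting, not data collection or conduct, so it should be closed before unblinding but does not undermine the trial.

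**What to change.** In Section 9.3:

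- Limit the mixed model of change to continuous outcomes. Allow a generalized mixed model for repeated visit-level indicators when events are not sparse, and define sparse in advance.
- For each safety event, report the number and percentage with at least one event by randomised arm, the risk difference with a Newcombe or exact 95% CI, and Fisher's exact p as descriptive.
- For repeatable events such as hypotensive episodes and AEs, also report rates per observed person-time, by Poisson or negative binomial regression with a log-time offset. If an arm has no events, give counts and person-time only, because the rate ratio is then not finite either.
- Reword the Table 2 item so that discontinuation of study drug is counted in both arms.

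The cost is a few sentences and slightly more analysis work, with no new data. The downside is wide safety intervals: at 36 per arm, even 4 v 0 events gives an interval from −0.6% to 25.3%.

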10. DATA COLLECTION AND QUALITY ASSURANCE

10.1. DATA COLLECTION FORMS

Data collected during interviews and exams will be documented on trial-specific data forms. Neuroimaging and ultrasound data will be saved in digital formats on a HIPAA-compliant server.

10.2. DATA MANAGEMENT

Once a subject is enrolled into the study, he/she will be assigned a unique identifier number and be referred to by initials and the study number only. Only research team members will have access to the files. Data will be entered on a web-based secure trial data system; the trial database will include for all variables an electronic data audit of data edits (who, when, and why). A data query report (including missing, out of range, and logic

checks) will be generated by the trial statistician. The investigators will keep subjects' medical records private as far as the law allows. The IRB and officials of the sponsor/funding agency will have access to these records as needed within legal guidelines. If study results are published in journals or presented at meetings, we will not use the subjects' names.

10.3. QUALITY ASSURANCE

10.3.1. TRAINING

Research personnel will be trained by the PI and co-investigators. The process of training on data forms completion, neuropsychological assessment and subject evaluation will be documented in a training log for each study personnel.

10.3.2. QUALITY CONTROL

To assess protocol compliance and quality of data collected, the PI along with another investigator will randomly and on intervals review data obtained. In addition, assessment of personnel competencies in obtaining data will be performed.

10.3.3. PROTOCOL DEVIATIONS

Every attempt will be exercised to maintain compliance with the approved study protocol. In the event when a deviation is noted, the Emory IRB will be notified as required by IRB Policies & Procedures only if the deviation affects the rights or welfare of subjects, the safety of subjects, the willingness of subjects to continue with study participation, or the integrity of the research data. The PI or designated personnel will conduct an investigation about the setting, reasons, and potential remedies that need to be instituted to rectify the deviation and prevent future similar instances.

11. PARTICIPANT RIGHTS AND CONFIDENTIALITY

11.1. INSTITUTIONAL REVIEW BOARD (IRB) REVIEW

This protocol and the informed consent document and any subsequent modifications will be submitted and reviewed by the Emory IRB.

11.2. CONSENTING PROCEDURE, INFORMED CONSENT FORMS, AND STUDY INFORMANTS

A signed consent form will be obtained from each participant or the participant's legally authorized representative. A single informed consent form will describe both the screening and study procedures. The consent form will describe the purpose of the study, the procedures to be followed, and the risks and benefits of participation. A copy will be given to each participant and this fact will be documented in the participant's study record.

During the consenting process, an assessment for decisional capacity to participate in clinical research will be performed. This is conducted by asking the subject a set of study-specific questions. A validated brief instrument for decisional capacity assessment will be administered:⁹¹ The University of California, San Diego Brief Assessment of Capacity to Consent (UBACC) instrument is a 10 item questionnaire that asks the participant about key areas of the informed consent. A score greater than 14.5 correlates with a score of greater than 16 on the MacArthur Competency Assessment Tool for Clinical Research (MacCAT-CR).⁹¹ MacCAT-CR is the most validated instrument in assessing decisional capacity in clinical research⁹² and a score greater than 16 has been traditionally considered adequate in prior NIH studies.⁹³

Participants who are unable to answer the capacity assessment questions correctly (UBACC score <14.5) may still qualify for the study but will need to have a surrogate and a study informant. The definition of the surrogate

will be consistent with the intent of the Common Rule (45 CFR 46, Subpart A). The following are, in order, possible surrogates:

(1) The person's agent designated by an advance health care directive.

(2) The conservator or guardian of the person having the authority to make healthcare decisions for the person.

- (3) The spouse of the person.
- (4) The domestic partner of the person as defined in Section 297 of the Family Code
- (5) An adult son or daughter of the person.
- (6) A custodial parent of the person.
- (7) Any adult brother or sister of the person.
- (8) Any adult grandchild of the person.
- (9) An available adult relative with the closest degree of kinship to the person.

When there are two or more available persons who are in different orders of priority pursuant to subdivision (c), refusal to consent by a person who is a higher priority surrogate shall not be superseded by the consent of a person who is a lower priority surrogate. That surrogate will need to consent to the study. If either party refuses, we do not enroll the subject. To ensure both the participant and the proxy understand the study protocol, we will ask subjects or legal next of kin to explain in their own words the nature of the study and the procedures involved.

The proxy will be considered the study informant if there is contact at least once a month. In some instances such as the lack of adequate contact by the surrogate or the surrogate's inability to complete the tasks of the study informant, the study informant may be a different individual as long as he/she is willing to provide information about the participant, and have contact with the participant for at least once a month (in person or telephone). The study informant will sign the study informed consent. If they are not available in person, the study staff will contact the informant to obtain needed information about the subject cognitive symptoms. In that case, a verbal consent will be obtained.

11.3. PARTICIPANT CONFIDENTIALITY

Only the investigators will have access to information about a particular subject. The subject's primary care physician will only be notified if the subject agrees. To maintain confidentiality, subject data will be referenced by number and stored in locked computer files and cabinets. Identifying information about a subject will not be used during the discussion, presentation, or publication of any research data. Only research team members will have access to the files. Data recorded and stored on the computer will be backed up to a disc and stored with the paper files. Participants will not be given any results of the research procedures unless there is a medical necessity. This will be clearly stated in the informed consent process.

11.4. PARTICIPANT COMPENSATION

Subjects will be compensated with gift cards for their effort and time at the following schedule:

- Screen Visit: \$25 + \$100 (for lumbar puncture procedure)
- Baseline Visits: \$100 (for visit + MRI) + \$75 for each PET scan (optional)
- Titration Visits (2): \$10
- 3 & 9 Month Follow Up Visits: \$25
- 6 Month Follow Up Visit: \$50 (cognitive testing, blood draw)

- 12 Month Follow Up Visits: \$100 (for visit + MRI) + \$75 for each PET scan (optional) + \$100 (for lumbar puncture procedure)
- Return Visit for blood redraw: \$20 and LP \$100 (as needed)
- Retinal Imaging: \$25Transportation: Up to \$30 for gas reimbursement and up to \$50 for taxi or shuttle service to the study site

11.5. STUDY DISCONTINUATION

The study may be discontinued at any time by the investigators, the Emory IRB, the OHRP or other government agencies as part of their duties to ensure that research participants are protected.

12. PUBLICATION OF RESEARCH FINDINGS

Publication of the results of this trial will be governed by the policies and procedures of the NIA and Emory.

